24	Participants with a history of or current cardiac arrhythmias (e.g. extrasystole, tachycardia at rest), history of risk factors for Torsade de Pointes syndrome (e.g. hypokalemia, family history of long QT Syndrome) or history or other clinical evidence of significant or unstable cardiac disease (e.g. angina, congestive heart failure, myocardial infarction, diastolic dysfunction, significant arrhythmia and/or coronary heart disease), moderate to severe valvular disease, or uncontrolled hypertension at screening	Exclusion criterion M10 met	Entered but did not satisfy criteria	Yes	No
25	Participants with any current or previous illness for which, in the opinion of the investigator and/or Sponsor, participation would not be in the best interest of the participant (e.g. compromise the well-being) or that could prevent, limit, or confound the protocol-specified assessments. This may include but is not limited to significant vascular, pulmonary (e.g. chronic obstructive pulmonary disease), gastrointestinal (e.g. significant diarrhea, gastric stasis, or constipation that in the investigator's opinion could influence drug absorption or bioavailability), endocrine (e.g. thyroid disease), neurologic, hematologic, rheumatologic, psychiatric, neoplastic, or metabolic disturbances. Any condition possibly affecting drug absorption (e.g. gastrectomy or other significant gastrointestinal tract surgery, such as gastroenterostomy, small bowel resection, or active enterostomy) will also lead to exclusion	Exclusion criterion M11 met	Entered but did not satisfy criteria	Yes	No

26	Participants who have received an organ transplant (except for skin, hair, or cornea transplants)	Exclusion criterion M12 met  Participants who have received an organ transplant (except for skin, hair, or cornea transplants)	Entered but did not satisfy criteria	Yes	No
27	Participants with any history of or current clinically significant skin disease requiring regular or periodic treatment	Exclusion criterion M13 met  Participants with any history of or current clinically significant skin disease requiring regular or periodic treatment	Entered but did not satisfy criteria	Yes	No
28	Participants with clinically relevant alcohol or drug abuse within 12 months of screening	Exclusion criterion M14 met  Participants with clinically relevant alcohol or drug abuse within 12 months of screening	Entered but did not satisfy criteria	Yes	No
29	Participants with history of clinically relevant drug rash	Exclusion criterion M15 met  Participants with history of clinically relevant drug rash	Entered but did not satisfy criteria	Yes	No
30	Participants who have taken any disallowed therapies as noted in Clinical Protocol Section 6.8, Concomitant Therapy, before screening or baseline. Participants who have taken IFN within the last 3 years prior to screening. Participants with lamivudine-refractory chronic hepatitis B.	Exclusion criterion A16 (adapted from M16) met  Participants who have taken any disallowed therapies as noted in Clinical Protocol Section 6.8, Concomitant Therapy, before screening or baseline. Participants who have taken IFN within the last 3 years prior to screening. Participants with lamivudine-refractory chronic hepatitis B.	Entered but did not satisfy criteria	Yes (only for IFN use in last 3 years and lamivudine refractory)	No
31	Participants with known allergies, hypersensitivity, or intolerance to JNJ-3989 or its excipients (refer to the IB [IB JNJ-3989 2020]) and/or to NA and/or to PegIFN- $\alpha$ 2a or their excipients (refer to the respective prescribing information).	Exclusion criterion A23 met  Participants with known allergies, hypersensitivity, or intolerance to JNJ-3989 or its excipients (refer to the IB [IB JNJ-3989 2020]) and/or to NA and/or to PegIFN- $\alpha$ 2a or their excipients (refer to the respective prescribing information).	Entered but did not satisfy criteria	Yes	No
32	Participants who meet any of the additional exclusion criteria for PegIFN- $\alpha$ 2a as described in local prescribing information (e.g. refer to Pegasys SmPC or Pegasys USPI) per the investigator's discretion.  Key exclusion criteria for PegIFN- $\alpha$ 2a include: 1 Participants with signs or symptoms compatible with autoimmune disorders 2 Participants with bone marrow suppression 3 Participants with hypoglycaemia, hyperglycaemia, and/or diabetes mellitus, who cannot be effectively controlled by medication 4 Participants with pre-existing ophthalmologic disorders 5 Participants with one or more of the following laboratory abnormalities: - Absolute neutrophil count <1,500 cells/mm  (<1,000 cells/mm  for black or African American participants) - Serum creatinine >1.5x ULN - Inadequately controlled thyroid function (thyroid stimulating hormone [TSH] and thyroxine [T4]) 6 Participants with pre-existing severe psychiatric conditions or a history of severe psychiatric disorders, including severe depression, suicidal ideation and attempted suicide.	Exclusion criterion A24 met  Participants who meet any of the additional exclusion criteria for PegIFN- $\alpha$ 2a as described in local prescribing information (e.g. refer to Pegasys SmPC or Pegasys USPI) per the investigator's discretion.	Entered but did not satisfy criteria	Yes	No

	Note: Contraindications to the use of PegIFN- $\alpha$ 2a need to be checked at screening and again at Week 12 for participants in Arm 2				
33	Disallowed from 3 years prior to screening until end of follow-up: IFN, other than the PegIFN- $\alpha$ 2a taken in the context of this study	Received protocol prohibited medication <specify medication and/or dose>	Received a disallowed concomitant treatment	If classified as major protocol deviation (reviewed case by case), excluded from PP set	Yes
34	Disallowed from 1 year prior to baseline until end of follow-up: Any oligonucleotide-based treatment (e.g. siRNA, nucleic acid polymers, antisense oligonucleotides), other than the study intervention taken in the context of this study	Received protocol prohibited medication <specify medication and/or dose>	Received a disallowed concomitant treatment	If classified as major protocol deviation (reviewed case by case), excluded from PP set	Yes
35	Disallowed from 6 months prior to screening until end of follow-up: Any investigational agent, investigational vaccine, invasive investigational medical device, or investigational biological product (other than the study intervention taken in the context of this study) Note: For investigational COVID-19 vaccines administered within 6 months prior to screening, an exception will be made as long as the vaccine has been approved (or received emergency use authorization or conditional marketing authorization) at the time of screening	Received protocol prohibited medication <specify medication and/or dose>	Received a disallowed concomitant treatment	If classified as major protocol deviation (reviewed case by case), excluded from PP set	Yes
36	Disallowed from 6 months prior to baseline until end of follow-up: Any systemically (e.g. intravenously, intramuscularly, orally, subcutaneously) administered medication that directly or indirectly interferes with immune responses (e.g. cyclosporine, interleukins, systemic corticosteroids exceeding 5 mg of prednisolone equivalent/day)	Received protocol prohibited medication <specify medication and/or dose>	Received a disallowed concomitant treatment	If classified as major protocol deviation (reviewed case by case), excluded from PP set	Yes
37	Disallowed from screening until end of follow-up: Any anti-HBV drug (including vaccines) other than the study intervention taken in the context of this study Notes: 
 
• NA standard of care treatment is allowed between screening and baseline
 
• Prior hepatic treatment with herbal or nutritional products is allowed but should be stopped at screening
 
	Received protocol prohibited medication <specify medication and/or dose>	Received a disallowed concomitant treatment	If classified as major protocol deviation (reviewed case by case), excluded from PP set	Yes
38	Disallowed from screening until end of study intervention: Products containing Hypericum perforatum (St. John's wort) -Biotin (>1 mg daily dose), either taken alone or as part of a multivitamin formulation Note: The use of other vitamins is allowed -Topical steroids (>7 days) under occlusive dressing	Received protocol prohibited medication <specify medication and/or dose>	Received a disallowed concomitant treatment	If classified as major protocol deviation (reviewed case by case), excluded from PP set	Yes
39	Approved COVID-19 vaccines or COVID-19 vaccines with conditional marketing	Subjects received approved COVID-19 Vaccine or COVID-	Received a disallowed concomitant treatment	If classified	Yes

	authorization, emergency use authorization or special approval for emergency are allowed during the study and within 2 days prior to PegIFN- $\alpha$ 2a administration during treatment phase 2	19 vaccine with conditional marketing authorization on the same day as PegIFN- $\alpha$ 2a administration		as major protocol deviation (reviewed case by case), excluded from PP set	
40	Dose of study medication JNJ-3989, not administered within scheduled time window	Subject missed JNJ-3989 dose(s)  If an injection of JNJ-3989 was missed, the injection should be given as soon as possible but within 3 weeks after the scheduled time. Otherwise, the injection should be skipped and the next injection should be given at the next scheduled time point per the initial injection schedule	Received wrong treatment or incorrect dose	If classified as major protocol deviation (reviewed case by case), excluded from PP set	Yes
41	If a dose of NA is missed, the participant should follow the guidelines in the prescribing information	Subject missed NA doses	Received wrong treatment or incorrect dose	If classified as major protocol deviation (reviewed case by case), excluded from PP set	Yes
42	Doses of study medication PegIFN- $\alpha$ 2a was missed	Subject missed 2 or more PegIFN- $\alpha$ 2a doses	Received wrong treatment or incorrect dose	If classified as major protocol deviation (reviewed case by case), excluded from PP set	Yes
43	Dose modifications of JNJ-3989 and NA (increase or decrease of dose level) are not permitted	Subject received modified dose of JNJ-3989 or NA	Received wrong treatment or incorrect dose	If classified as major protocol deviation (reviewed case by case), excluded from PP set	Yes
44	For PegIFN- $\alpha$ 2a, dose adjustment guidelines are recommended for participants who develop laboratory abnormalities during PegIFN- $\alpha$ 2a treatment, as recommended in the locally approved prescribing information for PegIFN- $\alpha$ 2a	Subject developed laboratory abnormalities but did not receive any PegIFN- $\alpha$ 2a dose adjustment  Recommended dose adjustments: -ANC <750 cells/mm  Reduce to 135 $\mu$ g -ANC <500 cells/mm  Discontinue treatment until ANC values return to more than 1,000 cells/mm  Reinstigate at 90 $\mu$ g and monitor ANC - Platelet <50,000 cells/mm  Reduce to 90 $\mu$ g - Platelet <25,000 cells/mm  Discontinue treatment	Received wrong treatment or incorrect dose	If classified as major protocol deviation (reviewed case by case), excluded from PP set	Yes
45	Subject stopped NA treatment at week 24, although some relevant changes in participant baseline status with regards to ALT, HBV DNA levels and/or HBeAg status were observed at Week 20 or any other event that in the opinion of the investigator could prevent stopping NA, were observed	Subject stopped NA treatment at week 24, although some relevant changes in participant baseline status with regards to ALT, HBV DNA levels and/or HBeAg status were observed at Week 20 or any other event that in the opinion of the investigator could prevent stopping NA, were observed	Received wrong treatment or incorrect dose	If classified as major protocol deviation (reviewed case by case), excluded	Yes

				from PP set	
46	Subject did not stop NA treatment at week 24, although no relevant changes in participant baseline status with regards to ALT, HBV DNA levels and/or HBeAg status or no other events that in the opinion of the investigator could prevent stopping NA treatment, were observed	Subject did not stop NA treatment at week 24, although no relevant changes in participant baseline status with regards to ALT, HBV DNA levels and/or HBeAg status or no other events that in the opinion of the investigator could prevent stopping NA treatment, were observed	Received wrong treatment or incorrect dose	If classified as major protocol deviation (reviewed case by case), excluded from PP set	Yes
	During the 48-week FU period, subject showed signs of decreasing liver function based on laboratory findings (e.g. International Normalized Ratio [INR], direct bilirubin) or clinical assessment (e.g. ascites, hepatic encephalopathy), but did not restart NA treatment	Subject has event of signs of decreasing liver function based on laboratory or clinical findings, but did not start NA treatment	Received wrong treatment or incorrect dose	If classified as major protocol deviation (reviewed case by case), excluded from PP set	Yes
47	During the 48-week FU period, subject has confirmed HBeAg seroreversion (HBeAg positive after it was negative at NA completion), but subject did not restart NA treatment	Subject has confirmed HBeAg seroreversion, but did not start NA treatment	Received wrong treatment or incorrect dose	If classified as major protocol deviation (reviewed case by case), excluded from PP set	Yes
48	During the 48-week FU period, subject has confirmed post-treatment increases in HBV DNA >2,000 IU/mL and ALT >5x ULN, over a period of at least 4 weeks, but subject did not restart NA treatment	Subject has a confirmed post-treatment increase in HBV DNA >2,000 IU/mL and ALT >5 x ULN over a period of at least 4 weeks, but did not start NA treatment	Received wrong treatment or incorrect dose	If classified as major protocol deviation (reviewed case by case), excluded from PP set	Yes
49	During the 48-week FU period, subject has confirmed has a confirmed post-treatment increase in HBV DNA >20,000 IU/mL over a period of at least 4 weeks, but subject did not restart NA treatment	Subject has a confirmed post-treatment increase in HBV DNA >20,000 IU/mL over a period of at least 4 weeks, but did not start NA treatment	Received wrong treatment or incorrect dose	If classified as major protocol deviation (reviewed case by case), excluded from PP set	Yes
50	Subject received incorrect injection treatment JNJ-3989	Received wrong treatment of study drug JNJ-3989: incorrect dose or placebo when randomized to active (and vice versa)	Received wrong treatment or incorrect dose	If classified as major protocol deviation (reviewed case by case), excluded from PP set	Yes
51	Subject withdrew consent but was not discontinued from the study treatment	Subject withdrew consent to the trial but was not discontinued from the study treatment	Developed withdrawal criteria but not withdrawn	Yes	No
52	The investigator believes that for safety or tolerability reasons (e.g. AE) it is in the best interest of the participant to discontinue investigational intervention, but the patient was not discontinued from the study treatment	Subject must discontinue the study treatment for safety reasons but subject continued study treatment	Developed withdrawal criteria but not withdrawn	Yes	No
53	The participant becomes pregnant but was not discontinued from the study treatment	Subject is pregnant but subject continued study treatment	Developed withdrawal criteria but not withdrawn	Yes	No

54	The participant has signs of hepatic decompensation (ie, clinical evidence of ascites, bleeding varices, or hepatic encephalopathy) or an increase in direct bilirubin >1.5x ULN in combination with INR $\geq$ 1.5x ULN or albumin <3.0 g/dL, but subject did not discontinue treatment with JNJ-3989 and the study	Subject has signs of hepatic decompensation (ie, clinical evidence of ascites, bleeding varices, or hepatic encephalopathy) or an increase in direct bilirubin >1.5x ULN in combination with INR $\geq$ 1.5x ULN or albumin <3.0 g/dL, but continued treatment	Developed withdrawal criteria but not withdrawn	Yes	Yes
55	The participant has a confirmed $\geq$ Grade 3 eGFR abnormality and a drop from baseline of >10 mL/min/1.73 m  , considered at least possibly related to JNJ-3989 (or PegIFN- $\alpha$ 2a, if applicable) that persists despite changing tenofovir disoproxil to ETV or TAF (if the patient was receiving tenofovir disoproxil) but was not discontinued from the study	Subjects has a confirmed $\geq$ Grade 3 eGFR abnormality and a drop from baseline of >10mL/min/1.73 m  , considered at least possibly related to JNJ-3989 (or PegIFN- $\alpha$ 2a, if applicable) that persists despite changing tenofovir disoproxil to ETV or TAF (if the patient was receiving tenofovir disoproxil) but continued treatment	Developed withdrawal criteria but not withdrawn	Yes	Yes
56	The participant has a QTcF prolongation (defined as a QTcF value of >500 ms, or an increase from baseline of >60 ms) at any given time point but was not discontinued from the study	Subject has a QTcF prolongation (defined as a QTcF value of >500 ms, or an increase from baseline of >60 ms) at any given time point but continued treatment	Developed withdrawal criteria but not withdrawn	Yes	No

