Assessments and sampling include efficacy (eg, HBsAg, HBeAg, and HBV DNA), safety (eg, [S]AEs, labs, ECGs, vital signs, physical examinations), PK, PK/ PD, viral genome sequencing, PBMC, human leukocyte

^a Kim BK, Revill PA, Ahn SH, et al. HBV genotypes: relevance to natural history, pathogenesis and treatment of chronic hepatitis B. *Antiviral Therapy*. 2011;16:1169-1186

antigen (HLA) typing, immunogenicity and pharmacogenomic samples, blood sampling for exploratory analysis of host and viral markers, and medical resource utilization.

The total duration of individual participation will be up to 72 weeks (screening not included). Participants will be considered to have completed the study if they have completed all the assessments of the end of study (EOS) visit (ie, FU Week 48).

An internal Data Review Committee (DRC) will be commissioned for monitoring safety of participants enrolled in this study. In addition, an Independent Flare Expert Panel (IFLEP) will be appointed.

NA Re-treatment Criteria During Follow-up

Participants who meet the protocol-defined NA treatment completion criteria (based on the Week 24 or FU Week 2 results) will be monitored closely during the follow-up period with a study visit at least once every 4 weeks. They should re-start NA treatment immediately in the event of:

- Signs of decreasing liver function based on laboratory findings (eg, International Normalized Ratio [INR], direct bilirubin) or clinical assessment (eg, ascites, hepatic encephalopathy).
- HBV DNA value of >1,000,000 IU/mL (irrespective of confirmation and/or ALT increase).

Note: A post-treatment HBV DNA value of >100,000 IU/mL should trigger re-testing of ALT/AST, HBV DNA, and total and direct bilirubin within a maximum of 7 days from receipt of the data and further repeats as necessary (ie, weekly until HBV DNA returns to <100,000 IU/mL). A post-treatment HBV DNA value of >20,000 IU/mL (but <100,000 IU/mL) should trigger a re-test within 14 days. At all times, additional re-testing of the above parameters should be performed at the investigator's discretion.

In addition, re-start of NA treatment should be considered in the following cases:

- Confirmed post-treatment HBeAg seroreversion (HBeAg positive after it was negative at NA completion), OR
- Confirmed (at least 4 weeks apart) post-treatment increases in HBV DNA >2,000 IU/mL and ALT >5x upper limit of normal (ULN), OR

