A13	
Criterion modified per Amendment 1
 
A13.1 Participants must have serum HBsAg >5 IU/mL at screening, as assessed by quantitative HBsAg assay.

A14	
Participants must have:
 
 a. Fibroscan liver stiffness measurement \leq9.0 kPa within 6 months prior to screening or at the time of screening, OR b. If a Fibroscan result is not available: a liver biopsy result classified as Metavir F0-F2 within 1 year prior to screening. 
Note: Other radiologic liver staging modalities (eg, acoustic radiation force impulse) might be used if standard practice at the site or if otherwise validated and agreed with the Sponsor. Results should be equivalent to Metavir F0-F2.
 
Note: Conventional imaging procedures (eg, conventional liver ultrasound, computed tomography [CT] or magnetic resonance imaging [MRI]) and serum marker panels are not allowed to rule out severe fibrosis or cirrhosis.

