6.5.1. NA Treatment Completion

All participants will receive the last dose of JNJ-3989 at Week 24 and the last dose of PegIFN- α 2a at Week 23 (Arms 1 and 2) or Week 11 (Arm 3). They will start the FU Period after the Week 24 visit. If all of the following NA treatment completion criteria are met based on the Week 24 results, treatment with NA will be stopped at the next scheduled visit (ie, FU Week 2):

- The participant has ALT <3x ULN, AND
- The participant has HBV DNA <60 IU/mL at Week 24 and HBV DNA <LLOQ at the previous visit, or HBV DNA <LLOQ at Week 24, AND
- The participant is HBeAg-negative, AND
- The participant has HBsAg <100 IU/mL.

Note: Participants who are close to meeting the protocol-defined NA treatment completion criteria with the Week 24 results, and do meet the criteria based on the FU Week 2 results may be allowed to stop NA at FU Week 4, after consultation with the Sponsor. In case of ALT elevation \geq 3x ULN at Week 24, the investigator must consider different potential causes of increased ALT to ensure appropriate work up and management as needed. If the ALT elevation is unrelated to HBV activity and/or <3x ULN by FU Week 2, NA completion may be considered at the discretion of the investigator and in consultation with the sponsor.

Participants who do not meet the above criteria based on the Week 24 or FU Week 2 results should continue NA treatment during the 48-week FU Period.

Participants who meet the above-mentioned NA treatment completion criteria will be monitored closely during the 48-week FU Period with a study visit at least once every 4 weeks. NA treatment should be re-started in accordance with the NA re-treatment criteria (see Section [6.5.2](#), NA Re-treatment Criteria During Follow-up, for more details).

The investigator should consider to re-start NA treatment per local standard of care at the EOS visit (Follow-up Week 48) for participants who met the NA treatment completion criteria based on the Week 24 (or FU Week 2) results, who did not re-start NA treatment during the follow-up phase, and who did not achieve and maintain HBsAg seroclearance. NA will not be provided by the sponsor after the final study visit.

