Safety	All participants who received at least 1 dose of study intervention within this ISA. Participants will be analyzed according to the study intervention they actually received.
Per Protocol Analysis Set (PP)	All participants in the FAS who do not have any of the selected major protocol deviations that may affect the assessment of efficacy in terms of the primary endpoint at Week 24. The selected major protocol deviations for efficacy analysis purposes that will be used to identify the participants included in the PP set are described in Section 6.4. Participants will be analyzed according to the study intervention they were randomly assigned to.
Pharmacokinetics Analysis Set	All participants who received at least 1 dose of study intervention and have at least 1 valid blood sample drawn for PK analysis.

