9	In the investigator's opinion, the participant is able to understand and comply with protocol requirements, instructions, and study restrictions and is likely to complete the study as planned per ISA (including the procedures outlined in the Master Protocol PLATFORMPAHPB2001)	Inclusion criteria M09 not met  In the investigator's opinion, the participant is able to understand and comply with protocol requirements, instructions, and study restrictions and is likely to complete the study as planned per ISA (including the procedures outlined in the Master Protocol PLATFORMPAHPB2001)	Entered but did not satisfy criteria	Yes	No
10	Male participants must agree to wear a condom when engaging in any activity that allows for passage of ejaculate to another person during the study intervention period and until 90 days after last dose of study intervention	Inclusion criteria A10(adapted from M10) not met  Male participants must agree to wear a condom when engaging in any activity that allows for passage of ejaculate to another person during the study	Entered but did not satisfy criteria	Yes	No

		intervention period and until 90 days after last dose of study intervention			
11	Female participants must agree not to donate eggs (ova, oocytes) for the purposes of assisted reproduction during the study intervention period and until 90 days after last dose of study intervention	Inclusion criteria A11 not met  Female participants must agree not to donate eggs (ova, oocytes) for the purposes of assisted reproduction during the study intervention period and until 90 days after last dose of study intervention	Entered but did not satisfy criteria	Yes	No
12	Male participants must agree not to donate sperm for the purpose of reproduction during the study intervention period and until 90 days after last dose of study intervention	Inclusion criteria A12 not met  Male participants must agree not to donate sperm for the purpose of reproduction during the study intervention period and until 90 days after last dose of study intervention	Entered but did not satisfy criteria	Yes	No
13	Participants must have serum HBsAg >100 IU/mL at screening, as assessed by quantitative HBsAg assay	Inclusion criteria A13 not met  Participants must have serum HBsAg >100 IU/mL at screening, as assessed by quantitative HBsAg assay	Entered but did not satisfy criteria	Yes	No

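### SAP Table 13 was not fully updated to protocol Amendment 1: row 13 still codes eligible participants with screening HBsAg above 5 and up to 100 IU/mL as deviators outside the per-protocol set, and the NA-stopping rows no longer match Section 6.5.1

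*SAP*

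**What the plan says.** SAP Section 1 ties the plan to protocol Amendment 1, and SAP Appendix 2 declares no changes to the protocol-planned analyses.

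SAP Table 2 defines the PP set as full-analysis-set participants free of "selected major protocol deviations that may affect the assessment of efficacy in terms of the primary endpoint at Week 24". SAP Section 6.4 makes Table 13 the list that decides those exclusions and adds an intercurrent-event flag to each row.

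- **Row 13 (criterion A13):** "Participants must have serum HBsAg >100 IU/mL at screening, as assessed by quantitative HBsAg assay". PP exclusion is Yes, without qualification; intercurrent event is No.
- **Protocol Section 5.1, A13.1 (modified by Amendment 1):** "Participants must have serum HBsAg >5 IU/mL at screening, as assessed by quantitative HBsAg assay".
- **Row 46:** the deviation begins "Subject did not stop NA treatment at week 24, although no relevant changes in participant baseline status with regards to ALT" and goes on to HBV DNA and HBeAg; HBsAg is not mentioned. Row 45 is the mirror case, stopping at Week 24 despite relevant changes. Both are flagged as intercurrent events, with PP exclusion only if the case is classed as major on individual review.
- **Protocol Section 6.5.1:** when the completion criteria are met on Week 24 results, "treatment with NA will be stopped at the next scheduled visit (ie, FU Week 2"), with FU Week 4 possible for those who qualify on FU Week 2 results. The criteria include HBsAg below 100 IU/mL, and participants who do not meet them continue NA. SAP Section 5.4.1.1.1 repeats the same criteria.

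**The concern.** Amendment 1 lowered the limit from 100 to 5 IU/mL so that response could be assessed over a wider baseline range, and it changed the primary endpoint to accommodate this. A PP set built from row 13 would take out the participants the amendment was written to admit. The supplementary estimand would then describe a narrower population than the protocol's, and the major-deviation tables would report eligibility failures that did not occur.

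Rows 45 and 46 raise a related problem. A participant whose HBsAg is 100 IU/mL or more and who continues NA as Section 6.5.1 directs can match row 46 if ALT, HBV DNA and HBeAg are unchanged. Rows 45 to 49 and the unnumbered liver-function row between rows 46 and 47 also concern events after the Week 24 assessment, yet they can remove people from a set defined for that assessment.

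**Working it through.** **1. Texts side by side**

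| Item | Current protocol | SAP Table 13 | Effect if applied as written |
|---|---|---|---|
| HBsAg at screening | above 5 IU/mL (A13.1) | above 100 IU/mL (row 13) | Eligible band above 5 to 100 is coded as a violation; PP exclusion unconditional |
| NA stop | FU Week 2 or 4, if criteria including HBsAg below 100 are met (6.5.1) | Week 24, judged on ALT, HBV DNA, HBeAg or other events (rows 45, 46) | Participants who follow 6.5.1 can be flagged; PP exclusion on review only |
| NA restart | Immediate at "HBV DNA value of >1,000,000 IU/mL (irrespective of confirmation and/or ALT increase") or declining liver function; to be considered for three other criteria (6.5.2) | Rows 47 to 49 and the liver-function row; no row for the HBV DNA limit | Texts do not correspond |
| Psychiatric exclusion | A24.1 adds a current disorder not controlled on stable medication | Row 32, item 6 lacks it | Older wording |

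Other rows point the same way. Row 7 cites the Master Protocol attachment on contraception where A07.1 cites the ISA appendix. Row 15 lacks the A01.1 sentence on antiretroviral treatment. Separately, row 59's description concerns treatment not being stopped, but its entered term says that it was.

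Row 13 cannot be deliberate, because SAP Table 8 plans a baseline HBsAg subgroup below 100 IU/mL.

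**2. The plan's own sample-size figures**

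These reproduce and are not in question.

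- Arm against fixed 2%: exact binomial, n = 30, one-sided 0.05/3 = 0.0167. Reject at 4 or more responders (size 0.003); power at 32% is 0.995, against the stated figure of more than 95%.
- Attrition: 30/(1 − 0.10) = 33.3, rounded up to 34 per arm, 102 in total.
- Pairwise 50% against 80%, n = 30, Hochberg over three comparisons: simulated power per comparison 0.67 to 0.68 with the third arm at 50% or 80%, against about 68% stated.

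**3. Size of the row 13 effect**

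Let f be the share with screening HBsAg above 5 and up to 100 IU/mL. It is not given, so it is an assumption. Number removed = 102f; PP size per arm = 34(1 − f).

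Pairwise power uses a normal approximation at one-sided 0.05/3 (z = 2.128), a stricter cut than Hochberg:

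Φ{[0.30 − 2.128·√(2·0.65·0.35/n)] / √[(0.25 + 0.16)/n]}

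| f | Removed of 102 | PP n per arm | Pairwise power | Power against 2% |
|---|---|---|---|---|
| 0 | 0 | 34 | 0.69 | 0.998 |
| 10% | 10 | 31 | 0.64 | 0.996 |
| 20% | 20 | 27 | 0.58 | 0.997 |
| 25% | 26 | 26 | 0.56 | 0.996 |

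The last column is not monotone because the exact rejection limit falls from 4 to 3 responders at the smaller sizes.

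**4. Shift in the PP response rate**

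Suppose the stratum above 100 IU/mL responds at 50% and the lower stratum at q. The rate over all eligible participants is (1 − f)·0.50 + f·q; the PP rate is 0.50. The difference is f·(0.50 − q). With q between 20% and 80%, this is at most 0.10 × 0.30 = 3 points at f = 10%, 6 points at 20% and 7.5 points at 25%, in either direction.

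**5. Reach into the main estimand**

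Row 13 is not an intercurrent event. For rows flagged as such, SAP Section 5.3.2 changes a result only when the Week 24 value is missing, and the main estimator already counts missing as non-response. The flag could alter handling only in the observed-case and LOCF sensitivity estimators, whose special rules cover participants without intercurrent events. That is a narrow route, closed by the timing sentence proposed below.

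**The case against.** The best defence is that little depends on this. The primary analysis uses the full analysis set. The SAP concedes that the PP analysis is biased and tabulates exclusions by arm and deviation type, so a cluster of row 13 exclusions would be seen. The list is to be finalized before lock. Row 13's entered term opens by saying that A13 was not met, so someone coding from the current protocol might never raise it. All of this limits the severity. It does not remove the error: the row states a replaced limit, carries no review step, and redefining PP after lock would be post hoc.

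Several stronger readings are tempting but unsupported:

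- **Compliant participants are dropped by the NA rows.** Rows 45 to 49 exclude only after case-by-case review, and row 46 exempts other events that the investigator thinks could prevent stopping. Participants are exposed to exclusion, not automatically removed.
- **Breaches of the HBV DNA 1,000,000 IU/mL rule go uncounted.** SAP Section 5.4.2.1.3 summarizes each re-treatment sub-criterion and cross-tabulates criteria met against NA restarted, and row 66 is a catch-all. The missing row is a gap in Table 13 only.
- **Rows 47 to 49 are wrong because restart is only to be considered.** For example, row 47 has "Subject has confirmed HBeAg seroreversion, but did not start NA treatment". Section 6.5.2 does say considered for that criterion, but Sections 2.3.3 and 4.2 say participants should restart when criteria are met. The protocol is itself inconsistent, so this is a matter for reconciliation.
- **Row 59 reverses the rule.** Its description and coded term show the intent; it is a wording slip.

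**Conclusion.** The concern holds for row 13 and, in weaker form, for the NA rows. Row 13 contradicts A13.1 and, followed literally, removes every participant eligible only because of Amendment 1 from the PP set. At an assumed share of 10% to 25%, that is about 10 to 26 of 102. Pairwise PP power would fall from 0.69 to between 0.64 and 0.56, and the PP response rate could differ from the all-eligible rate by up to 3 to 7.5 points under the assumed stratum rates. Power against the fixed 2% stays above 99%.

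Rows 45 and 46 conflict with protocol Section 6.5.1 and SAP Section 5.4.1.1.1 on timing and on HBsAg, with PP exclusion subject to review.

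A reader might infer that the primary result is at risk; it is not, for the reasons in step 5 of the working. The issue should be fixed, and its reach is essentially the PP supplementary estimand and the deviation tables. The documents do not say whether anyone enrolled under the earlier limit; for such a participant, 100 IU/mL was the applicable criterion.

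**What to change.** Before database lock:

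1. Set row 13 to the HBsAg limit in force when the participant enrolled, which is above 5 IU/mL under A13.1. A flat change would hide true deviations among anyone enrolled under the earlier limit.
2. Reconcile rows 45 to 49, the unnumbered liver-function row and the absent HBV DNA 1,000,000 IU/mL criterion with protocol Sections 6.5.1 and 6.5.2. The clinical team must also settle the protocol's differing wording on restart; this review takes no position on which rule is right.
3. State in SAP Section 6.4 that deviations arising only after the Week 24 assessment neither exclude from PP nor count as intercurrent events for the Week 24 endpoint.
4. Correct row 59's entered term and bring row 32, item 6 into line with A24.1. Rows 7 and 15 can be updated in the same pass.

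The cost is an edit to one SAP table, one added sentence, and re-coding of affected entries in the deviation system. No new data, change in sample size or change to the primary analysis is needed.
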